7.5.3.13 Adverse Events

All AEs will be recorded from the time the informed consent is signed through 12 weeks following the last dose of study drug, unless the subject enrolls in another clinical study of KRN23, is treated with commercially available KRN23, or is treated with KRN23 through another mechanism, at which point the collection of AEs within this study is no longer applicable. However, AEs will continue to be reported either under another KRN23 protocol or per post-approval requirements for safety monitoring, as applicable.

For subjects not continuing KRN23 treatment under commercial use or another mechanism upon completion of study drug treatment or early withdrawal from this study, a Safety Visit will be conducted 12 weeks \pm 1 week after the last dose of KRN23 in this protocol.

The determination, evaluation, reporting, and follow-up of AEs will be performed as outlined in Section 8.5. At each visit, subjects will be asked about any new or ongoing AEs since the previous visit. Assessments of AEs will occur at each visit to the investigational site and at Home Health Visits (KRN23 treatment arm only).

Clinically significant changes from baseline in physical examination findings, vital signs, clinical laboratory parameters, renal ultrasounds, eGFR, and ECGs will be recorded as AEs or SAEs, if deemed appropriate by the investigator.

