6 STUDY OBJECTIVES

Primary Objective:

- Evaluate the effect of KRN23 therapy in improving rickets in children with XLH compared with the active control (oral phosphate/active vitamin D)

Secondary Efficacy Objectives:

Evaluate the effects of KRN23 as compared with the active control on:

- Growth velocity and lower extremity deformity
- Pharmacodynamic markers that reflect the status of phosphorus homeostasis, including serum 1,25(OH)₂D, serum and urinary phosphorus, ratio of renal tubular maximum reabsorption rate of phosphate to glomerular filtration rate (TmP/GFR), and tubular reabsorption of phosphate (TRP)
- Biochemical markers of bone turnover that reflect rickets severity (alkaline phosphatase [ALP])
- Walking ability and patient-/parent-reported pain, fatigue, and physical function/mobility

Pharmacokinetic Objective:

Assess the PK of KRN23 throughout the dosing cycle

Safety Objective:

Evaluate the safety and tolerability profile of KRN23 in the treatment of children with XLH (aged 1 to ≤ 12 years), including adverse events (AEs) (eg, nephrocalcinosis), as compared with active control, and immunogenicity profile

Treatment Extension Period Objective:

To evaluate the long-term safety and efficacy of KRN23

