7.2 Discussion of Study Design, Including Choice of Control Group

The primary objective of this study is to evaluate the effect of KRN23 therapy on improving rickets in children with XLH compared with an active control (oral phosphate/active vitamin D therapy). Secondary efficacy objectives are to evaluate the effect of KRN23 compared with active control on growth velocity, lower extremity deformity (ie, bowing), changes in serum phosphorus and other PD markers, walking ability and patient-/parent-reported pain, fatigue, and physical function/mobility. Dental outcomes will be evaluated as an exploratory objective. The safety objective will be to establish the safety and tolerability profile of KRN23 in the treatment of pediatric patients with XLH, including AEs (eg, nephrocalcinosis), as compared with active control, and immunogenicity profile.

An open-label study design was chosen since blinding such a study would be problematic due to the different methods of administration and the individualized nature and frequent dose adjustments needed with oral phosphate/active vitamin D therapy.

Data from the ongoing pediatric Phase 2 study (UX023-CL201) helped establish the dose regimen and provided information for the design of this Phase 3 clinical trial in children with XLH. Interim data from the pediatric Phase 2 study suggested KRN23, administered Q2W at approximately 0.8 mg/kg for 40 weeks, increased serum phosphorus by an average of 0.7 mg/dL; increases of > 0.5 mg/dL were seen in 83.3% of subjects. Serum 1,25(OH)₂D concentrations and TmP/GFR levels also increased, demonstrating overall improved phosphorus homeostasis. The increases in serum phosphorus and 1,25(OH)₂D were sufficient to provide substantial healing of rickets. No subjects have experienced serum phosphorus levels above the upper limit of normal. The Q2W dosing regimen was chosen for this Phase 3 study because it appeared to produce a more stable and consistent increase in serum phosphorus levels with less fluctuation over time than the Q4W dosing regimen, and a safety profile that was not substantially different from the Q4W dosing regimen.

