7.5.3.6 Renal Ultrasound and Glomerular Filtration Rate

Renal ultrasounds will be conducted at the Screening Visit, and Weeks 24, 40, 64/EOS I, 88, 112, and 140/EOS II visits (or Early Termination). The ultrasound will be interpreted by qualified personnel at the central laboratory for purposes of inclusion criteria.

Baseline and all post-treatment renal ultrasounds will be evaluated by a trained central reader blinded to treatment assignment and subject data to evaluate changes in calcifications and all other renal abnormalities from baseline (.e, screening assessment). Ultrasonographic findings of nephrocalcinosis will be graded on a 5-point scale ([Verge et al. 1991](#)).

The eGFR will be calculated using the Bedside Schwartz equation ([Schwartz et al. 1976](#)) for determining creatinine clearance.

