7.6.5 Safety Analyses

Full Analysis Set will be used for the safety analysis. Subjects will be analyzed based on the actual treatment received. Safety variables including AEs, SAEs, safety laboratory assessments, vital signs, renal ultrasound, ECG, ECHO, and anti-KRN23 antibody will be summarized descriptively by treatment group.

All AEs will be coded using the Medical Dictionary for Regulatory Activities (MedDRA). The incidence and frequency of AEs will be summarized by System Organ Class, Preferred Term, relationship to study drug, and severity. All reported AEs with onset during the treatment (ie, treatment-emergent AEs) will be included in the analysis. For each AE, the percentage of subjects who experienced at least 1 occurrence of the given event will be summarized by treatment group. Special attention will be given to those subjects who died, discontinued treatment due to an AE, or experienced a SAE.

Clinical laboratory data will be summarized by the type of laboratory test. Reference ranges and markedly abnormal results (specified in the SAP) will be used in the summary of laboratory data. The frequency and percentage of subjects who experience abnormal clinical laboratory results (ie, outside of reference ranges) and/or clinically significant abnormalities (as determined by the Investigator) will be presented for each clinical laboratory measurement. The SAP will provide additional details on the planned safety analyses.

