7.2.3 Visit Time Windows

Unscheduled visit occurred prior to or on the date of initiation of the first dose will be mapped to the baseline visit if it is the last assessment prior to or on the date of initiation of the first dose; otherwise no mapping will be performed.

Unscheduled visits that occurred after the date of initiation of the first dose will be mapped to the post-baseline scheduled visit with the closest target study day (refer to Section 5.3 for study day definition and Appendix 3 for the schedule of events). If the unscheduled visit is in the middle of two scheduled visits, map to the later scheduled visit. For PD, PK and safety assessments (refer to Section 4.2, 4.3 and 4.4), if the time difference between the unscheduled visit and closest scheduled visit is ≥ 14 days, the unscheduled visit will not be mapped.

For descriptive summary tables, when more than one measurement is mapped to the same scheduled visit, the measurement taken on the scheduled visit will be used if it is not missing, otherwise the one closest to the target day will be used. If two or more visits have equal distances to the target day, then the later one will be used. If more than one measurement is collected on the same day, use the time or the sequence number to select the latest record.

For listings and shift tables in safety analysis, all data points will be included.

Early termination visit will generally follow the same rule as unscheduled visit except for a special case in X-rays. X-rays will not be performed at the early termination visit if the assessment was conducted within 3 months of termination. Hence if a subject has X-rays at both Week 40 and early termination visits, the X-rays on early termination visit will be mapped to Week 64.

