8.8.7 Renal Ultrasound

Renal ultrasound will be conducted with findings of nephrocalcinosis graded on a 5-point scale by a central reader. These results will be summarized by time point and presented by treatment group. Furthermore, a grade shift table summarizing changes from baseline by time point will also be created.

A listing of renal ultrasound/nephrocalcinosis scores will also be provided.

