8.8.8 ECG

Descriptive statistics for ECG parameters (heart rate, RR interval, PR interval, QRS duration, QT interval, and QTc) and changes from baseline values at each assessment time point to the end of study will be presented by treatment group. The QTc will be calculated using both the Bazett and Fridericia corrections.

ECG parameters will be summarized by study visit, by the maximum post-baseline value, change from baseline and maximum change from baseline. Shift from baseline to post-baseline visits in overall ECG assessment (normal or abnormal) will also be provided.

A listing of all ECG parameters including the overall assessment will also be created.

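### Blinded nephrocalcinosis grades are compared only visit by visit; the one count that accumulates within a child is adverse-event incidence, which rests on an unblinded investigator's discretion

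*Protocol*

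**What the plan says.** **Question.** Protocol section 6 sets a comparative safety objective, "including adverse events (AEs) (eg, nephrocalcinosis), as compared with active control, and immunogenicity profile". The same section heading in the SAP (2.4) repeats it.

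**Blinded route.** Protocol 7.5.3.6 schedules ultrasounds at Screening and Weeks 24, 40 and 64 in the controlled period, with later scans in the extension and one at early termination. Baseline and all post-treatment scans are "evaluated by a trained central reader blinded to treatment assignment and subject data to evaluate changes in calcifications", on a 5-point scale. SAP 4.3 lists the shift in this score as a safety endpoint. SAP 8.8.7 summarizes the grades by time point and arm, and adds that "a grade shift table summarizing changes from baseline by time point will also be created". Individual scores are listed. No worsening threshold, worst post-baseline grade or ever-worsened proportion is defined.

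**Adverse-event route.** Under Protocol 7.5.3.13, clinically significant changes in "renal ultrasounds, eGFR, and ECGs will be recorded as AEs or SAEs, if deemed appropriate by the investigator". The investigator is unblinded; Protocol 7.2 explains that "An open-label study design was chosen since blinding such a study would be problematic". SAP 8.8.1 tabulates subject incidence of the events to monitor by preferred term and arm, and SAP Appendix 10 lists nephrocalcinosis under ectopic calcification.

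**Inference.** Protocol 7.6.5 says that "renal ultrasound, ECG, ECHO, and anti-KRN23 antibody will be summarized descriptively by treatment group". SAP 8.1 has a general rule of 95% CIs for between-group differences; the ultrasound section does not apply it.

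**The concern.** The protocol's rationale sections say that oral phosphate supplementation raises the risk of nephrocalcinosis, so this is a central safety contrast. A clinician or regulator will ask how many children on each treatment got worse during the 64 weeks. The blinded grades could answer that, but no planned table adds them up within a child. The figure that does accumulate is adverse-event incidence. It depends on whether someone who knows the arm, and the expectation about the control drug, judges a scan change worth recording. If that figure is the only cumulative one in the report, it is likely to be read as the answer.

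**Working it through.** **1. Number of children.** The documents give no planned figure for nephrocalcinosis. The one stated figure, 60 children, comes from the primary endpoint (Protocol 7.6.1) and only sets the arm size. A two-sample t-test with difference 1.80 − 1.40 = 0.40, SD 0.50, two-sided alpha 0.05 and power 0.80 needs 26 per arm. Then 26/0.90 = 28.9, so 29 per arm and 58 in total, against the stated 60. I use 30 per arm, or 30 × 0.90 = 27 after the planned 10% dropout.

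**2. What each route counts.**

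| | Blinded? | Per child at one visit? | Accumulates within a child? |
|---|---|---|---|
| Shift table (SAP 8.8.7) | yes | yes | no |
| Adverse-event incidence (SAP 8.8.1) | no | not its purpose | yes |

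**3. By-visit tables do not fix the ever-worsened number (illustration).** Take three scans, each with 3 of 30 children worse. If they are the same children, 3 ever worsened (10%). If they are different children every time, 3 × 3 = 9 did (30%). At 5% per visit the range is 5% to 15%; at 15% it is 15% to 45%. Newcombe 95% intervals for the two extremes:
- 9/30 − 3/30 = 20 points (−0.5 to 39.0)
- 3/30 − 3/30 = 0 points (−16.9 to 16.9)

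Both situations can produce identical by-visit counts.

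**4. The Week 64 shift as a substitute.** It equals the ever-worsened count only if worsening persists and the child is still scanned at Week 64. Protocol 7.3.3.1 takes a child off study when clinically meaningful worsening of mineralization is judged related to study drug, and Protocol section 4 defines study drug as KRN23. Read literally, the rule can remove worsened children from later visits in one arm only. For example, if 3 of 30 KRN23 children worsen by Week 24 and one is discontinued, the scheduled Week 64 scans can show at most 2 of those 3, among 29 (6.9% rather than 10%).

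**5. Early-termination scans.** SAP 7.2.3 treats them like unscheduled visits. A safety assessment 14 days or more from the closest scheduled visit is not mapped. Yet the same section says: "For listings and shift tables in safety analysis, all data points will be included". A scan at Week 32 lies (32 − 24) × 7 = (40 − 32) × 7 = 56 days from either neighbouring planned ultrasound. The SAP does not say which row of a by-time-point table holds it, or how two scans at one time point are counted.

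**6. Discretionary recording (illustration).** Assume true worsening of 20% in both arms.
- 80% against 50% recorded: 0.20 × 0.80 = 16% and 0.20 × 0.50 = 10%, a false 6-point difference
- 60% against 40% recorded: 12% and 8%, a false 4-point difference
- Equal recording: no false difference

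The documents support neither a size nor a direction for this.

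**7. Precision of the blinded any-time proportion.** With equal true rates p, the half-width of the 95% interval is 1.96 × √(2p(1 − p)/n):

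| p | n = 27 | n = 30 |
|---|---|---|
| 5% | 11.6 | 11.0 |
| 10% | 16.0 | 15.2 |
| 20% | 21.3 | 20.2 |
| 30% | 24.4 | 23.2 |

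(percentage points)

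**The case against.** A reader might infer that the adverse-event table is the only per-child nephrocalcinosis count, or that the plan yields no unbiased comparison. The documents do not support either reading. At each visit the shift table places every scanned child in one baseline-by-visit cell, from blinded reads and by arm. That comparison is descriptive and imprecise, but unblinding does not bias it. Nor is it right that intervals are ruled out, given the general rule in SAP 8.1. The difficulty is that no ultrasound proportion is defined for that rule to act on.

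Other points on that side have weight:
- Nine different children would require each earlier worsening to have reversed by the next scan. Nothing in the documents suggests this, and the animal summary in Protocol 5.2.2 says reversibility could not be shown. The upper end of the range is therefore a bound, not an expectation.
- The listing of scores would let a reader rebuild the cumulative count in 60 children. That is true, but the worsening rule would then be chosen with open-label data in view.
- Discretion has limits. Protocol 8.5.4.1 requires new or worsening conditions to be documented, and an independent committee with nephrology expertise monitors safety. Neither replaces a blinded cumulative count by arm.
- Double counting needs an extra scan, and none is planned. The all-data-points sentence also keeps early-termination scans in view, which is desirable.

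SAP 8.8.8 summarizes ECG "by the maximum post-baseline value, change from baseline and maximum change from baseline". Those are continuous measures, so this is no strict precedent for an ordinal grade, but it shows that an across-visit summary per child is within the SAP's practice.

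**Conclusion.** The concern holds in a limited form. Blinded, per-child, by-arm information exists at Weeks 24, 40 and 64. What is missing is a defined worsening threshold and a blinded any-time proportion by arm with an interval. The only cumulative count within a child therefore passes through unblinded judgment. The Week 64 shift cannot safely stand in for it, because discontinuation for worsening may remove children and early-termination scans have no stated place.

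The size cannot be taken from the documents. The 3-to-9 range and the recording percentages are illustrations under assumed rates, and whether recording would in fact differ by arm is unknown. The change is worth making because it is cheap and serves a comparison that the objectives name; it is not a flaw that invalidates the safety analysis.

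**What to change.** Add one table to SAP 8.8.7: the number and percentage of children with at least a 1-grade increase over Screening in the blinded central grade at any ultrasound through Week 64. Include early-termination and unscheduled scans, count each child once, and show results by arm with the risk difference and a 95% CI (Newcombe, for example). State that this table, read alongside the by-visit shift tables, is the main comparative nephrocalcinosis summary and that adverse-event incidence is supportive.

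The cost is one table from data already collected, with no change to visits, procedures or clinical rules. The downsides are a wide interval at about 30 children per arm, and some reader noise, since an any-visit rule counts a single stray upgrade in either arm.

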7.5.4 Exploratory Assessments

7.5.4.1 Health-related Quality of Life

Individuals with XLH are affected by skeletal abnormalities which may impact their physical and mental health status. The SF-10 for Children Health Survey (SF-10) is a caregiver-completed questionnaire designed to assess physical and psychosocial health-related quality of life in healthy and ill children ([Saris-Baglana et al. 2006](#)). The 10 items were adapted from the Child Health Questionnaire and utilize a 4-week recall period. Responses are used to generate 2 component summary scores: physical summary score (PHS-10) and psychosocial summary score (PSS-10). Higher global scores are associated with better quality of life. The SF-10 will be administered in subjects \geq 5 years of age at the Screening Visit during the Baseline visit (Week 0), and Weeks 24, 40, 64/EOS II, 88, 112, and 140/EOS II (or Early Termination). If a subject is $<$ 5 years of age at the Screening Visit and therefore has no baseline data, SF-10 will not be administered even when the subject turns 5 during the study. Every attempt should be made to ensure that the responder completing the first administration completes subsequent administrations to minimize variability.

7.5.4.2 Dental Evaluation

Some children with XLH may present with severe dental defects, which typically manifest as spontaneous infections leading in dental abscesses ([Carpenter et al. 2011](#)). These infections

are a result of defective dentin and enamel hypoplasia that diminishes the layer surrounding the pulp chamber, enabling oral bacteria to enter the pulp chamber and form abscesses.

Dental evaluations will be conducted to assess the number of dental events from dental caries, delay in eruption of the dentition, enamel hypoplasia, dental abscesses, and gingivitis. At each clinic visit, an oral examination will be conducted by the investigator and subjects will be proactively asked if they had any dental events such as dental caries, tooth extraction, root canal, dental abscesses, and gingivitis.

7.5.4.3 Pre- and Post-prandial Serum Phosphorus and Calcium Concentrations Substudy

Pre- and post-prandial serum phosphorus and calcium concentrations will be assessed at a single clinic visit anytime 10 to 14 days after a KRN23 dose. The substudy will be conducted at sites in the US, Canada, and Australia that are able to provide and observe a nutritionally defined meal in their clinic. The substudy will be conducted in approximately 20 subjects, age ≥ 3 years.

The Investigators or Study Coordinators at the sites chosen will contact the subject/caregiver asking for participation in the substudy. If agreed, a clinic visit will be scheduled and the subject will be consented at that time and prior to any substudy assessments being conducted. The clinic visit may take the place of a Home Health visit or be at a regularly scheduled clinic visit. Before the visit at which the substudy assessments are conducted, subjects must have received at least 4 doses of KRN23 (≥ 8 weeks of treatment) with at least 80% compliance and did not miss the previous dose of KRN23.

Subjects will fast overnight for a minimum of 8 hours, and fasting serum will be collected prior to breakfast ([Table 7.5.4.3.1](#)). Meals will contain predefined ranges of phosphate, calories, and carbohydrate and will be representative of a typical Western diet for children. Subjects will have the option of 2 to 3 nutritionally defined meals (depending on the clinical site). Subjects will be given a 1-hour window to consume the meal. Dietary phosphate will be estimated based on the amount of food consumed. Serum samples will be drawn 1 and 2 hours after the completion of the meal.

Table 7.5.4.3.1: Schedule of Events for the Pre- and Post-prandial Serum Phosphorus Concentrations Substudy

	Prior to Substudy Assessments	Hour 0	Hour 1	Hour 2	Hour 3
Informed consent	X				
Serum phosphorus and calcium ¹		X			
Begin meal ²		X			
End meal ³			X		
Serum phosphorus and calcium ⁴				X	X

1. Serum collected after at least 8 hours of fasting and before meal.
2. Nutritionally defined meal typical of a Western diet for children with a known phosphate content (approximately 200 to 500 mg).
3. Meal should be completed within 1 hour. If the meal cannot be completely consumed, record the quantity consumed.
4. Serum collected 1 and 2 hours after completion of the meal.

7.5.5 Appropriateness of Measurements

The assessments and timing of assessments used in this study, and the variables analyzed, are typical of those used to evaluate healing and severity of rickets, as well hypophosphatemia, renal reabsorption, and vitamin D metabolism in subjects with XLH. The primary goals of treatment in pediatric XLH patients are to correct or minimize rickets/osteomalacia, radiographic abnormalities, and skeletal deformities and improve growth outcomes (Carpenter et al. 2011). KRN23 binds to and inhibits FGF23. FGF23-mediated hypophosphatemia plays leads to rickets in children with XLH. Therefore, change in rickets in the KRN23 group will be the primary endpoint in this study.

Radiographs are routinely recommended during the initial evaluation of XLH, and to evaluate healing of rickets and skeletal deformities. Performance measures such as the 6MWT (≥ 5 years old at the Screening Visit) in subjects have been successfully used in other clinical development programs. Additionally, age-appropriate, patient-reported outcome were included to assess functional disability, pain, and health-related quality of life (ie, PROMIS Pediatric Pain Interference, Fatigue and Physical Function Mobility; FPS-R; and SF-10 in subjects ≥ 5 years old at the Screening Visit).

Additional assessments are included both as PD measures and safety indicators of potential secondary complications associated with treatment, including serum phosphorus, serum calcium, 1,25(OH)₂D, and urinary calcium and creatinine, as hypercalciuria may occur in the absence of hypercalcemia.

Intact PTH (iPTH) levels and Tmp/GFR are routinely measured as a part of oral phosphate/active vitamin D therapy in XLH, as secondary hyperparathyroidism is common. Biochemical markers of bone turnover that reflect rickets severity (eg, alkaline phosphatase

[ALP]) may provide an indication of treatment effect. The relatively extensive panel of biomarkers has been included in this Phase 3 study to provide the most information on relevant clinical laboratory parameters for endpoint confirmation and analysis. Where possible, timing of assessments has been coordinated with standard safety laboratory tests to minimize risk and discomfort and avoid unnecessary duplication of testing.

The safety parameters to be evaluated in this study include standard assessments such as recording of medical history, AEs and SAEs, physical examination, vital signs, serum chemistry, concomitant medications, and other routine clinical and laboratory procedures. Routine, non-invasive procedures will provide relevant indicators of possible renal and cardiac risk; renal ultrasounds will be used to detect any calcinosis in susceptible organs. Since elevated free FGF23 has been associated with left ventricular hypertrophy (LVH) in patients with chronic kidney disease, ECGs will examine the potential risk in XLH subjects.

The study will be conducted in a pediatric population, as such additional safety measures including Home Health care visits (KRN23 treatment arm only) and a DMC have been incorporated into the study design. Where possible, measures to minimize pain and distress to the subject have been considered for this study protocol.

